## 10. RATIONALE FOR ADHERENCE MONITORING

### Real-time dried blood spot intraerythrocytic TFV-DP drug level monitoring

In the iPrEx study, assessments of adherence both by self-report and sensitive drug level assays on blood plasma and PBMCs suggested a strong correlation between adherence to the daily intervention and efficacy (49, 50). The low overall level of adherence to daily pill-taking in the study was striking, with detectable drug found in 9% of seroconverters, and only 51% of non-seroconverters. The medication adherence data is in stark contrast to the overall study retention (86-88% at 48 weeks), and self-reports of medication adherence (95%). Analyses designed to adjust for adherence suggest that if TDF/FTC were taken with fidelity on a daily basis, there could be preventive efficacy of over 90% (8).

The STRAND study established plasma and PBMC steady-state tenofovir (TFV) drug levels achieved from directly observed dosing of TDF/FTC twice weekly, four-times weekly, and 7-times weekly. With twice-weekly dosing, mean PBMC levels were 11 fmol/mL, 4 days per week yielded 32 fmol/mL, and 7 days per week (daily) dosing yielded 42 fmol/mL. In iPrEx, seroconverters had PBMC drug levels on average of 11 fmol/mL, suggesting fewer than two doses per week on average. Non-seroconverters had mean PBMC levels of 16 fmol/mL. A model created from the iPrEx data calculating the protective efficacy which was likely at a given drug concentration in PBMCs demonstrated that the PBMC drug level at which 90% protection would be achieved was estimated to be 16 fmol/mL. Correlating the iPrEx model data with the STRAND data, two doses per week would be estimated to result in 76% (95% CI 56-96%) efficacy; four doses per week, 96% (95% CI, 90- >99%); seven doses per week (daily dosing), 99% (95% CI 96- >99%) (51).

The Partners-PrEP study (a population of heterosexual serodiscordant men and women in Kenya and Uganda) also found that drug levels strongly predicted TDF/FTC and TDF efficacy - detectable drug (using a more sensitive assay than the primary iPrEx data) predicted 86% efficacy for TDF alone, and 90% efficacy for TDF/FTC (contrast 67% and 75%, in the overall population, respectively). The Partners-PrEP study found three distinct patterns of adherence: 1. Seventy percent of participants had sustained TFV drug levels >40 ng/mL; 2. Ten percent of the population had levels that were detectable most of the time (10-40 ng/mL), but dipped occasionally to undetectable levels; and 3) Twenty percent of the population had persistently undetectable drug levels (52). It is probable that prospective, real-time identification of these non-adherent populations (although it remains unclear what percentage this would represent in iPrEx [the MSM population studied to date] – one would suspect the overwhelming majority) and applying intensive adherence interventions would be critical to the success of a PrEP effort.

In this study we will use intracellular TFV-DP from DBS as our primary outcome measure of adherence. Anderson and Castillo-Mancilla have developed technology using LC-MS/MS to measure intra-erythrocytic TFV-DP levels, which provide a measure of average tenofovir exposure (adherence) over the preceding 30-90 days, not unlike a Hemoglobin A1C measurement (53). Such measurements can be made from DBS samples, which are stable over time and easy to handle. The key characteristic that enables TFV-DP to be used as an adherence biomarker is the 17-day half-life of TFV-DP in red blood cells. A similar long-term objective measure of adherence, tightly correlated with virologic suppression has been validated using scalp hair samples (54). However, sampling of scalp hair has proven variably acceptable among diverse populations (unpublished data, ACTG A5257).

## 11. RATIONALE FOR DEMONSTRATION PROJECT

Daily oral PrEP with TDF/FTC as part of a combination prevention package has been shown to be effective for HIV prevention in randomized controlled trials of MSM and heterosexual men and women at risk of HIV infection (55-57). However, some studies in African women have shown lack of efficacy that is believed in large part due to inadequate PrEP adherence (11, 58). In addition, pharmacokinetic studies in women suggest that near-perfect adherence for TDF/FTC oral dosing may be more critical for protection against vaginal compared with rectal exposures. Taken together, these results imply that women may require substantially greater levels of adherence to oral TDF/FTC to effectively decrease HIV acquisition. Therefore, interventions to optimize adherence are particularly vital to maximizing the protective efficacy of PrEP for women. Although current FDA approval and CDC clinical guidelines for oral TDF/FTC as PrEP include at-risk women as candidates, limited clinical data exists on the use of PrEP in US women. Further research is needed to advance effective implementation, particularly taking into account the known challenges to achieving and maintaining high levels of adherence for women.

[figure not shown]
**This pilot demonstration project is a single-arm, open-label, longitudinal study of oral TDF/FTC as part of a combined prevention package in heterosexual women age 18 years or older and are HIV-uninfected at project entry and at-risk of HIV acquisition.** We will evaluate adherence to and acceptability of once-daily oral TDF/FTC as PrEP among HIV-uninfected women in Southern California who are at increased risk of HIV acquisition. Los Angeles and San Diego represent two of the top three counties in California of number of reported HIV/AIDS cases. In combination, they total half of the number of HIV cases in the state supporting the need for ongoing prevention efforts in all at-risk populations. Working in tandem, the LAC-PATH and CCTG partnership provides a unique opportunity to further collaborative research that has been fostered within the CHRP funding

structure, capitalizing on the strengths of existing individual projects in MSM and transgender women. The LAC-PATH group will enroll 85 women and the CCTG group will enroll 50 women for a total of 135 participants across five clinical sites in Los Angeles and San Diego counties. These clinical sites currently provide services to a racially and ethnically diverse population and will enable outreach to potential female participants disproportionately affected by the HIV/AIDS epidemic, with a focus on African-American and Latina women. Given the centrality of adherence to PrEP efficacy in women, this protocol sets forth a multi-modal, intensive strategy to support PrEP delivery that involves innovatively combining the use of technology, therapeutic drug monitoring and behavioral counseling.

Subsequent to the publication of the iPrEx results, the CDC issued clinical guidance for clinicians for the use of PrEP in MSM (59). These included practical guidelines for testing and follow-up, albeit in the absence of data for any other schedule for follow-up than the one used in the iPrEx study, which entailed monthly HIV-testing, laboratory monitoring, and adherence and risk-reduction counseling, and serve as the basis for screening and monitoring in this project.

Combination prevention services must be designed to be easily accessible, non-judgmental, community-based, culturally, ethnically, and linguistically appropriate to the relevant populations, and accessible regardless of ability to pay or insurance/documentation status. They will also provide vital linkages to ancillary support services, sexual risk reduction counseling, routine HIV testing, preconception planning and primary health care.

In its initial pilot project, five community-based sites will serve as facilities at which participants may present for screening for pre-exposure prophylaxis services, as well as sexually transmitted diseases. At the sites, eligibility criteria will be assessed, HIV, STD and laboratory testing will be performed, an initial 1-month supply of PrEP medication will be provided, and referrals will be initiated. All participants who are provided an initial 1-month supply will be required to return to the site for ongoing treatment, follow-up testing, adherence counseling, risk-reduction programming, and other appropriate referrals. Follow-up will be on a monthly basis for the first month, and then de-escalated to an every-3-month follow-up interval. Follow-up with participants by phone and email will be used as appropriate to maximize program retention.

**12. ENROLLMENT OF PARTICIPANTS**

Potential participants will be screened for a combination prevention intervention. After the participant reviews and signs the informed consent document, receives HIV testing (including 4th generation test or ELISA and nucleic acid amplification (NAAT) testing) to confirm HIV-uninfected status, and is evaluated using the inclusion and exclusion criteria, she will be considered enrolled in the protocol.

**13. INCLUSION CRITERIA**

**(All must be satisfied)**

Individuals who will be at most benefit from PrEP are individuals who are at recurrent and substantial risk for acquiring HIV infection.

At-Risk Criteria (at least one):

- 1) Condomless sex in the last 3 months with one or more male partners of unknown HIV status known to be at substantial risk of HIV infection (IDU, bisexual, sex for goods, recently incarcerated, from a country/ region with HIV prevalence >1%, interpersonal Partner Violence);

- 2) STI (rectal or vaginal gonorrhea or syphilis) diagnosis during the last 6 months.
- 3) Previous post-exposure prophylaxis (PEP) use during the last 12 months.
- 4) Has at least one HIV-infected sexual partner for  $\geq 4$  weeks.
- 5) Sex for exchange of money, goods or services

Other inclusion criteria:

- Female at birth and identifies as female gender
- Age 18 years or older
- Able to understand and provide consent in English or Spanish
- HIV negative by 4th generation test (Ag/Ab test) or combination of EIA and HIV RNA
- Creatinine clearance  $\geq 60$  ml/min (via Cockcroft-Gault formula)

## 14. EXCLUSION CRITERIA

Pregnancy at enrollment.

Any condition, which in the opinion of the provider, will seriously compromise the participant's ability to comply with the protocol, including adherence to PrEP medication dosing, such as active, untreated or unstable major mental illness (i.e. untreated psychotic disorder).

Use of prohibited medications, in particular, agents known to be nephrotoxic or drugs slow in renal excretion (as detailed in the MOPS)

Previous participation in an HIV vaccine trial. Participants that were documented to have received only placebo are not excluded.

Signs or symptoms suspicious for Primary HIV Infection (PHI). If the participant presents with symptoms consistent with PHI, such participants should be referred to expert HIV clinical care immediately for further evaluation and treatment. For management of suspected PHI, see Section 26.3.

## 15. STUDY ENROLLMENT PROCEDURES

Enrollment may only be initiated in person. To enroll, a participant must present to one of the clinical site facilities.

### 15.1. Screening

At a screening visit, Informed Consent will be reviewed. An intake of inclusion and exclusion criteria will be performed by program personnel. HIV-testing (4th generation test, or EIA and HIV RNA) and screening laboratories as noted in the Schedule of Evaluations (SOE) will be performed. If all inclusion and no exclusion criteria are met, a baseline visit will be scheduled within 28 days. A detailed locator form will be completed including primary contact telephone, paper-mail, email, social-network, and emergency contact information. This information will be verified at each subsequent visit for changes and/or updates. At screening, individuals will also be asked to complete a brief computer assisted self-interview (CASI)-based assessment evaluating HIV risk; PrEP awareness, barriers and facilitators; and willingness to take PrEP.

### 15.2. Baseline Visit

At the baseline visit, a needs assessment, including a CASI-based sexual risk assessment will be conducted. Although the intent is that the CASI is entirely self-administered, research staff will be available to assist participants who have questions about

operation of the CASI instrument or content. Initial STI testing and coordination of necessary referral services will be performed. Fertility intentions also will be assessed. All women who meet criteria for use will be offered daily oral TDF/FTC as part of a combination prevention package. A patient identification number (PID) will be assigned to each patient screened for the study. PIDs will include site code and be formatted to be compatible with the YoungLabs data core. PIDs will not be reassigned even if the participant fails to enter the study. The PID must be included on every CRF and participant specimen during the study. Each site must maintain a master list of PIDs in a central location. The patient registration and inclusion/exclusion CRF must be completed on the online system. Procedures in the study visits are shown in the schedule of evaluations (Section 18).

## **16. REGIMENS, ADMINISTRATION, AND DOSING**

The PrEP regimen to be used will be TDF/FTC, provided as a fixed-dose combination tablet as Truvada®. Dosing of TDF/FTC is one tablet by mouth once daily. For participants with creatinine clearance <60 mL/min or on hemodialysis, TDF/FTC should not be used. No other regimen is available or recommended in the event of intolerance or adverse events attributable to TDF/FTC.

In the event of toxicity, intolerance, or allergy, see Toxicity Management, below.

### **16.1. High Risk Exposures While on PrEP**

In the event of a clinical indication for 3-drug PEP participants will be referred to locally available PEP services and may resume protocol participation upon completion of the PEP medications course with documentation of HIV-uninfected status at or after 4 weeks of PEP provision.

### **16.2. Missed Dose Instructions**

A missed dose should be taken when remembered on a given calendar day. Instructions to participants will be not to take more than one tablet daily regardless of missed doses.

### **16.3. Duration of Therapy**

TDF/FTC should be taken daily for 48 weeks (336 days). Participants may receive study treatment until their last study visit. Further plans for continued availability of TDF/FTC for PrEP after the first 48 weeks will be determined based on the results of the current pilot demonstration study.

### **16.4. Drug Supply, Distribution, and Accountability**

TDF/FTC (emtricitabine 200mg/tenofovir 300mg) will be available in bottles of 30 tablets to be taken as one tablet by mouth daily. Site pharmacies will be responsible for dispensing a 4-week supply of TDF/FTC at the baseline visit, an 8-week supply of TDF/FTC at the 4-week follow-up visit, and a 12-week supply of TDF/FTC at the 12-week, 24-week, and 36-week follow-up visits, in appropriate packaging based on manufacturer's instructions (USP equivalent tight containers). Pharmacies at sites will be responsible for documentation of all medication dispensation, and tracking of all program-related medications.

Participants *must* follow-up at the site of enrollment to receive the remaining treatment course and associated testing and services. Further supplies will *not be re-dispensed* in the event that medication is lost.

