### **16.5.1. Real-time intraerythrocytic drug levels**

Blood will be collected for intraerythrocytic TFV-DP drug level assays at each follow-up visit. Prior pharmacokinetic/pharmacodynamics studies have established levels for categorization of dosing for interpretation of DBS levels. Given the high adherence requirement for women to achieve protective levels, a threshold of 1050 fmol/punch corresponding to 6 or more doses per week will be used as the threshold for optimal adherence (28, 60). Levels below this threshold will be considered to represent suboptimal adherence and will trigger intensification of adherence support as outlined below.

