Daily dosing reminders will be sent for the duration of the study. Both reminder timing and message content can be individualized and will be arranged at the baseline visit. The study coordinator will work with the participant to select and refine 10 personal reminders from a list of pre-determined reminders that cover various themes shown to be effective in improving adherence (i.e., social support, loss frame, health gain) as well as 5 categories of factoids (i.e., food, history, science). Participants will receive 2 personal reminders and 5 factoids each week for the duration of the study. These themes will be developed through focus groups and targeted group feedback. Participants can choose to create their own reminders if they prefer, and messages can be modified throughout the course of the study. The coordinator will work with each participant individually to ensure that adherence reminders are programmed to be sent at times consistent with when the patient typically takes her medication. Reminder times can vary for different days of the week to accommodate for changes in schedule (e.g., 8 M-F, and 10 AM on Sat/Sun). Once the preferred dosing time is identified, the text reminder system is automated. Patients will confirm medication taking via text responses to the personalized reminders. If a participant does not respond on three consecutive occasions, a high alert message (chosen by the participant) will be sent. If the participant does not respond to this message, the study coordinator will initiate phone calls to contact the participant to determine reason for no-reply. At any point, if a participant initiates a text that is not one of the expected responses, the study team will review that text and contact the subject if there is a concern. Participants will be informed not to use texting for emergencies. The content/reasons for iTAB requests for assistance will be documented and summarized post study,

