## 20. SCHEDULE OF CLINICAL AND LABORATORY EVALUATIONS

Table 1. Schedule of Evaluations							
	Screen	Study Weeks of Follow-up				Interim	
	Within 28 days	Baseline	Wk 4	Week 12 and every 12 weeks	End of Study or premature D/C	Suspected HIV or STI infection	Interim for Missed Visit
Visit Window		± 14 days					
Informed Consent	X						
Demographics	X						
Locator Form	X						
Medical/Medication History	X						
Concomitant medications	X	X	X	X	X	X	X
Limited physical exam	X	X	X	X	X	X	X
Clinical assessment	X	X	X	X	X	X	X
Fertility intent assessment	X	X	X	X	X	X	X
Contraceptive counseling	X	X	X	X	X	X	X
Domestic/partner violence assessment	X	X	X	X	X	X	X
Systems review and iTAB setup		X					
PrEP dispensation		X	X	X			
Adherence/ risk reduction/ Sexual health counseling		X	X	X	X	X	X
Self-reported tablet assessments 	X	X	X	X	X	X	X
PrEP adherence assessment			X	X	X	X	X
Laboratory							
HIV EIA/VL or Ag/Ab 	X						
Rapid HIV Test		X	X	X	X	X	X
HBsAg and HBsAb	X						
Urine beta HCG	X	X	X	X	X	X	X
Cr and GFR	X		X	X	X	X	X
LFT and CBC		X					
Serum RPR		X		[X]	[X]	X	[X]
3-site STI Screening		X		[X]	[X]	X	[X]
HSV-2 Screening		X			X 		
DBS for RBC TFV-DP			X	X	X	X	X
Banked plasma specimen 			X	X	X	X	X
HIV RNA, CD4, genotype						X	
Whole blood						X	

Table 1. Schedule of Evaluations							
	Screen	Study Weeks of Follow-up				Interim	
	Within 28 days	Baseline	Wk 4	Week 12 and every 12 weeks	End of Study or premature D/C	Suspected HIV or STI infection	Interim for Missed Visit

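### Section 16.4 supplies exactly 336 days of drug with no margin for late visits, so a woman who takes every tablet and attends late but in window can be without PrEP before her blood spot

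*Combined protocol and SAP*

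**What the plan says.** Section 16.3 sets the course: "TDF/FTC should be taken daily for 48 weeks (336 days). Participants may receive study treatment until their last study visit". It attaches no extra quantity to the second sentence.

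Section 16.4 has pharmacies "dispensing a 4-week supply of TDF/FTC at the baseline visit, an 8-week supply of TDF/FTC at the 4-week follow-up visit", followed by 12 weeks' supply at each of weeks 12, 24 and 36. The drug "will be available in bottles of 30 tablets", but the section does not say whether tablets are counted out to 28, 56 and 84 or handed over as whole bottles. Section 11 says that "an initial 1-month supply of PrEP medication will be provided". Lost drug is not replaced.

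Table 1 (section 20) gives a visit window of ±14 days. The table is flattened and the value appears once; I read it as applying to all follow-up visits. The "PrEP dispensation" row is marked at baseline, week 4 and the 12-weekly visits, not at the interim visits. A blood spot is taken at every follow-up visit.

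On levels under 1,050 fmol/punch, section 16.5.1 says: "Levels below this threshold will be considered to represent suboptimal adherence and will trigger intensification of adherence support as outlined below". Section 16.5.3 sends a repeat low to PrEP-STEPS. Section 30.2 bases the primary analysis on women on PrEP, censors temporary and permanent discontinuation, and compares drug levels before and after the intensified interventions.

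**The concern.** Supply equals the nominal course to the day, while the schedule lets each visit run two weeks over. The only women certain to run out are those who do what the protocol asks and take a tablet every day.

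Three things follow. First, women enrolled because they are at risk of HIV lose drug through scheduling alone, in a protocol that argues women need near-perfect adherence. Second, section 16.5.1 reads a level below 1,050 as behaviour, with no exception for exhausted supply, so counselling goes to women whose dosing was not the problem. Third, such a level enters the comparison around the intensified interventions as a low starting value, and its recovery after resupply would look like a response to counselling.

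**Working it through.** **Inputs.** Supplies of 4, 8, 12, 12 and 12 weeks and bottles of 30 (16.4); course of 336 days (16.3); window ±14 days (Table 1); threshold 1,050 for 6 or more doses a week (16.5.1); half-life 17 days (section 10); mean of 1,352 at about 6 of 7 doses in an MSM and transgender-women trial (16.5.2).

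**1. The plan's own total.** 28 + 56 + 84 + 84 + 84 = 336 days, as in section 16.3. Whole bottles would give 30 + 60 + 90 + 90 + 90 = 360 tablets.

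**2. Largest gap before each sample.** With one tablet a day, unused tablets carried forward and earlier visits on time: gap = max(0, last in-window day − tablets dispensed before that visit).

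| Visit | Last in-window day | Exact counts: tablets, gap | Whole bottles: tablets, gap |
|---|---|---|---|
| Week 4 | 42 | 28, 14 days | 30, 12 days |
| Week 12 | 98 | 84, 14 days | 90, 8 days |
| Week 24 | 182 | 168, 14 days | 180, 2 days |
| Week 36 | 266 | 252, 14 days | 270, none |
| Week 48 | 350 | 336, 14 days | 360, none |

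A gap begins at 1 day late with exact counts. With bottles it begins at 3, 7 and 13 days late for weeks 4, 12 and 24. The gaps are alternatives: one late visit shifts later supply, so the total per woman is at most 14 days (exact) or 12 days (bottles).

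**3. Level after the gap.** The documents give no steady state for daily dosing in women. I assume a range from 1,050 × 7/6 = 1,225 to 1,352 × 7/6 = 1,577. The lower end treats a category cutoff as the typical 6-dose level, so it is a low bound. With first-order kinetics, level = SS × (1 − 2^(−days dosed/17)) × 2^(−gap/17).

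- Week 12, exact: (1 − 2^(−84/17)) × 2^(−14/17) = 0.967 × 0.565 = 0.547, giving 670 to 862.
- Week 12, bottles: (1 − 2^(−90/17)) × 2^(−8/17) = 0.703, giving 862 to 1,109. This is below 1,050 only if SS is under 1,050/0.703, about 1,490.
- Weeks 24 to 48, exact: about 691 to 891.
- Weeks 24 to 48, bottles: 1,128 to 1,453 at week 24, and full steady state later.
- Week 4: 471 to 607 (exact) or 530 to 682 (bottles). Even with no gap, the day-28 level is only 0.681 × SS = 834 to 1,074, so week 4 is low largely because accumulation is incomplete.

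**4. Rebound on resupply.** Take the exact-count week 12 sample on day 98, then daily dosing to day 168. Level = SS − (SS − start) × 2^(−70/17), with 2^(−70/17) = 0.0576.

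- SS 1,225: 1,225 − 555 × 0.0576 = 1,193, a rise of 523.
- SS 1,577: 1,577 − 715 × 0.0576 = 1,536, a rise of 674.

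Neither involves any change in behaviour.

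**5. How often a run-out puts a daily taker below 1,050.** The documents give no attendance pattern, so these shares are illustrative. With independent uniform timing over ±14 days, the share of daily takers is:

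- Week 12: 10 to 30% (exact), 0 to 13% (bottles).
- Week 48: 1.6 to 9.1% (exact), 0% (bottles).

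Triangular timing centred on the due date gives 3.6 to 22.5% or 0 to 4.4% at week 12, and 0.5 to 7.6% or 0% at week 48.

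**The case against.** Whole bottles are at least as natural a reading of section 16.4 as counted tablets, and they supply 24 tablets more than the course needs. On that reading weeks 24 to 48 stay above 1,050 and only weeks 4 and 12 have a material gap. This stands, and it limits the effect on measurement. It does not remove the gaps of up to 12 and 8 days in the first 12 weeks.

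The affected group is narrow. At 6 doses a week with earlier visits on time, a woman runs out only at week 4, where 28 tablets last 28 × 7/6 = 32.7 days against day 42. An empty bottle may also prompt attendance, so uniform timing may overstate the shares. Both points stand.

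Section 28.1 says inadvertent interruptions should be resumed quickly, and section 30.2 censors temporary discontinuation. A run-out could fit that class, but neither section names one before an in-window visit. Section 28.1 acts only after the gap, and its HIV retest applies only beyond 14 days without dosing. Targeted iNSC asks what prevented dosing, so a run-out would probably surface there, after the trigger. The MOPS, which is not in the documents, might hold a buffer, but 16.4 fixes the quantities itself. The later formal SAP could settle the analysis rule but not the tablets.

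A reader might infer that the low readings are false. They are not: they measure exposure correctly, and only the reading of them as behaviour is wrong.

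**Conclusion.** The point holds as a supply and interpretation problem, and it should be fixed. The gap in protection follows from the protocol's own numbers and rests only on reading the window as covering all follow-up visits. It depends on neither the kinetic model nor the censoring rule.

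The misdirected counselling and the rebound in the before-and-after comparison need a level below 1,050. At week 12 that can happen across the whole assumed steady-state range with exact counts, but only at its lower part with bottles. Week 4 cannot be attributed to supply alone.

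A reader might go further and infer that the week 48 proportion is materially understated. If exact counts are used, no such woman is censored, every adherent woman takes a tablet daily and visits are uniform in the window, an expected 90% would become 0.90 × (1 − 0.016) = 88.6% to 0.90 × (1 − 0.091) = 81.8%. The documents establish none of those four conditions, and with whole bottles the figure does not move. That reading is not supported.

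**What to change.** In section 16.4, state the number of tablets per visit and dispense 14 extra at baseline, carried forward. With exact counts, cumulative supply becomes 42, 98, 182, 266 and 350 days, equal to the last in-window day of each visit. With bottles it becomes 44, 104, 194, 284 and 374. No in-window gap remains under either practice. A full extra bottle would also work, but it exceeds the window and loosens the link between supply and HIV, creatinine and pregnancy testing.

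In section 30.2, flag any blood spot drawn after supply ended. The inputs already exist or are easily asked for: "Pharmacies at sites will be responsible for documentation of all medication dispensation", and for the last-dose date "Patients will confirm medication taking via text responses to the personalized reminders", or a question at the visit. State whether a run-out counts as temporary discontinuation. Report the proportion above 1,050 with and without flagged levels, and do not use a flagged level as the pre-intervention value.

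Cost: 14 × 135 = 1,890 tablets, or 1,890 / (336 × 135 = 45,360) = 4.2%, some wording, and slightly more drug held by participants between tests. The overage does not correct incomplete accumulation at week 4.
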